5.2.2 Serious Adverse Events (Immediately Reportable to the Sponsor)

A serious adverse event is any adverse event that meets any of the following criteria:

- Is fatal (i.e., the adverse event actually causes or leads to death)
- Is life threatening (i.e., the adverse event, in the view of the investigator, places the patient at immediate risk of death)

This does not include any adverse event that, had it occurred in a more severe form or was allowed to continue, might have caused death.

- Requires or prolongs inpatient hospitalization (see Section [5.3.5.12](#))
- Results in persistent or significant disability/incapacity (i.e., the adverse event results in substantial disruption of the patient's ability to conduct normal life functions)
- Is a congenital anomaly/birth defect in a neonate/infant born to a mother exposed to study drug
- Is a significant medical event in the investigator's judgment (e.g., may jeopardize the patient or may require medical/surgical intervention to prevent one of the outcomes listed above)

The terms "severe" and "serious" are not synonymous. Severity refers to the intensity of an adverse event (e.g., rated as mild, moderate, or severe, or according to National Cancer Institute Common Terminology Criteria for Adverse Events [NCI CTCAE]; see Section 5.3.3); the event itself may be of relatively minor medical significance (such as severe headache without any further findings).

Severity and seriousness need to be independently assessed for each adverse event recorded on the eCRF.

Serious adverse events are required to be reported by the investigator to the Sponsor immediately (i.e., no more than 24 hours after learning of the event; see Section 5.4.2 for reporting instructions).

5.2.3 Adverse Events of Special Interest (Immediately Reportable to the Sponsor)

Adverse events of special interest are required to be reported by the investigator to the Sponsor immediately (i.e., no more than 24 hours after learning of the event; see Section 5.4.2 for reporting instructions). Adverse events of special interest for this study are as follows:

- Cases of potential drug-induced liver injury that include an elevated ALT or AST in combination with either an elevated bilirubin or clinical jaundice, as defined by Hy's Law (see Section 5.3.5.7)
- Suspected transmission of an infectious agent by the study drug, as defined below
 - Any organism, virus, or infectious particle (e.g., prion protein transmitting transmissible spongiform encephalopathy), pathogenic or non-pathogenic, is considered an infectious agent. A transmission of an infectious agent may be suspected from clinical symptoms or laboratory findings that indicate an infection in a patient exposed to a medicinal product. This term applies only when a contamination of the study drug is suspected.
- Any adverse event leading to discontinuation of study drug
- New or worsening neurologic signs and symptoms that are consistent with a diagnosis of progressive multifocal leukoencephalopathy
- Suspected or confirmed COVID-19 infection
- *Grade ≥2 thromboembolism or deep vein thrombosis*

5.3 METHODS AND TIMING FOR CAPTURING AND ASSESSING SAFETY PARAMETERS

The investigator is responsible for ensuring that all adverse events (see Section 5.2.1 for definition) are recorded on the Adverse Event eCRF and reported to the Sponsor in accordance with instructions provided in this section and in Sections 5.4–5.6. It is preferred, but not required, that the clinician who assesses adverse events not be the

same clinician who assesses UC or CD efficacy outcomes (e.g., PROs and endoscopic evaluation).

For each adverse event recorded on the Adverse Event eCRF, the investigator will make an assessment of seriousness (see Section 5.2.2 for seriousness criteria), severity (see Section 5.3.3), and causality (see Section 5.3.4).

5.3.1 Adverse Event Reporting Period

Investigators will seek information on adverse events at each patient contact. All adverse events, whether reported by the patient or noted by study personnel, will be recorded in the patient's medical record and on the Adverse Event eCRF.

After informed consent for study entry has been obtained but prior to initiation of study drug, only serious adverse events caused by a protocol-mandated intervention (e.g., invasive procedures such as biopsies, discontinuation of medications) should be reported (see Section 5.4.2 for instructions for reporting serious adverse events).

After informed consent for study re-entry has been obtained (see Section 3.1.3) but prior to initiation of study drug, only serious adverse events caused by a protocol-mandated intervention (e.g., invasive procedures such as biopsies, discontinuation of medications) or prior study treatment should be reported (see Section 5.4.2 for instructions for reporting serious adverse events).

After initiation of study drug following study entry or study re-entry, all adverse events will be reported until 8 weeks after the final dose of study drug.

Any adverse event that occurs after completion of Week 52 and required safety follow-up assessments but prior to obtaining informed consent for study re-entry should be captured on the General Medical History and Baseline Conditions eCRF rather than the Adverse Event eCRF, unless it is a serious adverse event related to prior study treatment.

Instructions for reporting adverse events that occur after the adverse event reporting period are provided in Section 5.6.

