3.1.2 Efmarodocokin Alfa Administration

Patients enrolled in the extension study will receive efmarodocokin alfa treatment or undergo observation for up to approximately 2 years (through Week 104), as determined on the basis of the patient's disease status, as outlined in [Table 2](#). Upon entry into the extension study, patients will receive efmarodocokin alfa 60 µg/kg IV Q4W or undergo observation, depending on their disease status at the time of their last endoscopy in the parent study. The first dose of efmarodocokin alfa in the extension study may not be administered less than 2 weeks after last dose of study drug in parent study. During the extension study, patients will receive efmarodocokin alfa 60 µg/kg IV Q4W or undergo observation, depending on their disease status at a scheduled visit or a disease evaluation visit (details on disease evaluation visits are provided in [Section 3.1.5](#)).

Table 2 Efmardocokin Alfa Treatment Algorithm

Patient's Disease Status	Action to Be Taken
Meets criteria for clinical remission ^a	
Discontinue efmardocokin alfa (if applicable)Undergo observation and assessments per schedule of activities (see Appendix 1)
Does not meet criteria for clinical remission ^a	
Receive efmardocokin alfa 60 µg/kg IV Q4W until clinical remission is achieved ^bUndergo assessments per schedule of activities (see Appendix 1)
Meets criteria for disease flare ^c (off treatment) after entry into study	
Consult with Medical Monitor to determine appropriate course of action prior to administration of efmardocokin alfa (if applicable)
Experiences disease worsening as a result of efmardocokin alfa treatment, in the investigator's judgment, or disease flare while receiving efmardocokin alfa ^c	
Permanently discontinue efmardocokin alfaInitiate rescue therapy at discretion of investigatorUndergo safety follow-up assessments 8 weeks after final dose of efmardocokin alfa ^d

Q4W=every 4 weeks.

^a Clinical remission during the extension study, as defined in Section [3.1.4.3](#).

^b First dose of efmardocokin alfa in the extension study to be administered no less than 2 weeks after last dose of study drug in parent study

^c Disease flare during the extension study, as defined in Section [3.1.4.4](#).

^d See Section [3.1.6](#) and [Appendix 1](#) for details regarding safety follow-up.

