5.4.2 Reporting Requirements for Serious Adverse Events and Adverse Events of Special Interest

5.4.2.1 Events That Occur prior to Study Drug Initiation

After informed consent for study entry has been obtained but prior to initiation of study drug, only serious adverse events caused by a protocol-mandated intervention should be reported. After informed consent for study re-entry has been obtained (see Section 3.1.3) but prior to initiation of study drug, only serious adverse events caused by a protocol-mandated intervention or prior study treatment should be reported. The paper Clinical Trial Serious Adverse Event/Adverse Event of Special Interest Reporting Form provided to investigators should be completed and submitted to the Sponsor or its designee immediately (i.e., no more than 24 hours after learning of the event), by faxing the form using the fax number provided below:

Region	Fax Number
North America	[contact]
Europe, Middle East, Africa, or Asia Pacific	[contact]

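### Before the first extension dose, the first-entry reporting rule omits SAEs attributed to parent-study treatment, although the parallel re-entry rule includes SAEs from prior study treatment

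*Combined protocol and SAP*

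**What the plan says.** The reporting rules in Section 5.3.1 come in layers.

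- The opening paragraph is general: every adverse event is to be entered in the medical record and on the Adverse Event eCRF.
- At first entry the rule narrows: "After informed consent for study entry has been obtained but prior to initiation of study drug, only serious adverse events caused by" a protocol-mandated intervention are reportable. The examples given are invasive procedures and the stopping of medications.
- At re-entry for Year 2 the matching sentence has the same limit but ends "discontinuation of medications) or prior study treatment should be reported".
- Full collection starts later: "After initiation of study drug following study entry or study re-entry, all adverse events will be reported until 8 weeks after the final dose".

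Section 5.4.2.1 repeats the first-entry limit ("only serious adverse events caused by a protocol-mandated intervention should be reported"), and so does the adverse event footnote to Appendix 1. In both places the re-entry sentence again adds prior study treatment.

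On the patient pathway, Section 3.1.2 assigns patients at entry by disease status at their last parent-study endoscopy. For those in remission, Table 2 says: "Undergo observation and assessments per schedule of activities". Section 3.2 puts treatment or observation at up to about 2 years. Footnote b to Table 3 foresees patients who complete Week 52 without any efmarodocokin alfa in the extension. Section 1.3 names parent-study responders to efmarodocokin alfa as an intended group, partly to learn how long remission lasts off drug.

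**The concern.** The study's purpose is long-term safety. Section 5.1.1 describes risks that could appear late: epithelial tumor promotion, and neutralizing antibodies whose effects might persist. A patient exposed in a parent study and then only observed is one in whom a late effect could surface. Appendix 1 schedules adverse event checks at this patient's visits, yet the first-entry rule does not make an SAE attributed to the earlier drug reportable.

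Section 5.7 states that no serious reactions are currently expected, so any treatment-emergent SAE judged related to the drug is handled as a SUSAR. A related SAE that an investigator does not report could therefore be a missed expedited report, and that investigator would still be following the protocol.

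**Working it through.** The point rests on text, so the check sets the provisions side by side.

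**1. The two rules**

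| Place | First entry, before dosing | Re-entry, before dosing |
|---|---|---|
| 5.3.1 | Intervention-caused SAEs only | Same, plus prior study treatment |
| 5.4.2.1 | Intervention-caused SAEs only | Same, plus prior study treatment |
| Appendix 1 footnote | Intervention-caused SAEs only | Same, plus prior study treatment |

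The omission is consistent across all three, so it is not a slip in one place. Sections 4.5.2 and 5.3.1 also keep SAEs related to prior study treatment on the Adverse Event eCRF between the end of Year 1 follow-up and re-entry consent, when the patient is not in the study. A consented patient under observation in Year 1 therefore has narrower coverage than one who has temporarily left.

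**2. How long the narrower rule lasts.** It ends at the first extension dose. A patient who loses remission and is dosed leaves it then. A patient who stays in observation remains under it to Week 104.

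**3. Whether another provision closes the gap**

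- *5.4* lists SAEs for 24-hour reporting regardless of relationship, but refers to 5.4.2 for the requirements, and 5.4.2.1 contains the limit.
- *5.4.2.2* starts reporting of adverse events of special interest only after study drug initiation.
- *5.3.5.9* ties deaths to the reporting period in 5.3.1.
- *5.3.5.4* carries over only events still ongoing when the parent study ended.
- *5.1.2.3* asks that signs of malignancy be reported to the sponsor, with no dosing condition. It asks for expedited reporting of signs of thromboembolism through 5.2.3, which leads back to 5.4.2. Its serious infection paragraph has no comparable instruction.
- *5.6* asks for related SAEs after a period ending 8 weeks after the final dose of study drug. Section 2 defines study drug as efmarodocokin alfa without restricting it to extension doses, so parent doses could be counted. But 5.3.1 ties initiation to study entry or re-entry, and the Appendix 1 footnote places the 5.6 duty after that initiation. Even on the wider reading, the first 8 weeks after the last parent dose are not covered. A patient can enter within them, since 3.1.2 allows extension dosing from 2 weeks after the last parent dose.

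None of these clearly closes the gap, though several conflict with the limit.

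**4. Size.** The plan's SAE figures are the intervals in 6.1 for 135 evaluable patients. Exact (Clopper-Pearson) intervals reproduce them: 6.6% gives 3.05% to 12.19% (stated 3% to 12%), and 13.5% gives 8.23% to 20.44% (stated 8% to 20%). They do not size this gap. The documents do not say how many patients were treated with efmarodocokin alfa in a parent study and then only observed, nor give a rate of drug-related SAEs in them.

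**The case against.** The strongest reply is that little is lost in practice. The opening of 5.3.1 has all adverse events recorded on the eCRF, and the limiting sentences speak of what is reported. Malignancy and thromboembolism have instructions of their own. Section 5.6 can be read to reach parent doses. At first entry the prior treatment was given under a parent protocol, whose own follow-up rules may apply, and that could explain the different wording. Undosed patients are outside the safety population in 6.4, so no planned table changes. The tumor risk is described as hypothetical, and no treatment-emergent antibodies were found in the Phase Ib study.

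Much of this stands, and it rules out three stronger readings.

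- A reader might infer that the study collects no such events. The recording sentence and 5.1.2.3 do not support that; the defect is contradictory instructions.
- A reader might try to size the gap by applying the 6.6% and 13.5% rates in 6.1 to some share of the 48 + 270 = 318 potentially eligible patients. Those rates are placebo-arm rates for all SAEs, not only drug-related ones. The 318 is a pool that enrollment may not reach, and no share staying undosed is given. The wider wording would also add only SAEs attributed to prior treatment.
- A reader might infer that many of the observed patients will be efmarodocokin alfa remitters. The documents give no breakdown, and placebo and vedolizumab patients may also enter in remission.

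The reply does not remove the conflict. An investigator faced with *only* in three places has a clear textual basis for not reporting. The parent protocols are not among the documents, so their coverage cannot be assumed.

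**Conclusion.** The point holds as a gap and an inconsistency in the reporting rules. At first entry, an SAE attributed to parent-study treatment is not reportable on the literal wording until the first extension dose, which for an observed patient may never come within the roughly 2 years. The re-entry sentence shows that the sponsor accepts the wider principle.

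The harm is to signal detection and expedited reporting. The safety tables planned in 6.4 are not affected, because they include only dosed patients. The number of patients and events cannot be computed from the documents. The conclusion assumes that initiation of study drug in 5.3.1 means extension dosing, as the text there and in Appendix 1 indicates. Whether any event is finally lost to the sponsor depends partly on the parent protocols.

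**What to change.** - In 5.3.1, 5.4.2.1 and the Appendix 1 adverse event footnote, extend the first-entry sentence to SAEs caused by prior study treatment, as the re-entry sentence already does. State that this includes parent-study treatment, blinded or unblinded. The last words matter because 4.2 keeps the parent assignment blinded until the parent study is unblinded.
- Reconcile 5.6 with this, saying whether its period runs from parent doses, extension doses or both.
- Reconcile the opening sentence of 5.3.1 with the limits below it, so that sites know what is recorded and what is reported before dosing. Align the malignancy and thromboembolism instructions in 5.1.2.3 with the same rule.
- In 6.4, add a separate listing of these events, apart from those in the dosed safety population.

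The cost is one phrase in three places, the reconciling edits, one listing, and a few more SAE reports from visits that already take place.

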4.5.3 Physical Examinations

A complete physical examination, performed at baseline in the extension study (Study Week 0) and other specified visits, should include an evaluation of the head, eyes, ears, nose, and throat, and the cardiovascular, dermatologic, musculoskeletal, respiratory, GI, genitourinary, and neurologic systems. Any abnormality identified at baseline should be recorded on the General Medical History and Baseline Conditions eCRF.

Limited, symptom-directed physical examinations, including an abdominal examination, should be performed at specified postbaseline visits and as clinically indicated.

Changes from baseline (Study Week 0) abnormalities should be recorded in patient

notes. New or worsened clinically significant abnormalities should be recorded as adverse events on the Adverse Event eCRF.

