5.3.5.9 Deaths

All deaths that occur during the protocol-specified adverse event reporting period (see Section 5.3.1), regardless of relationship to study drug, must be recorded on the Adverse Event eCRF and immediately reported to the Sponsor (see Section 5.4.2). This includes death attributed to progression of UC or CD.

Death should be considered an outcome and not a distinct event. The event or condition that caused or contributed to the fatal outcome should be recorded as the single medical concept on the Adverse Event eCRF. Generally, only one such event should be reported. If the cause of death is unknown and cannot be ascertained at the time of reporting, "**unexplained death**" should be recorded on the Adverse Event eCRF. If the cause of death later becomes available (e.g., after autopsy), "unexplained death" should be replaced by the established cause of death. The term "**sudden death**" should not be used unless combined with the presumed cause of death (e.g., "sudden cardiac death").

If the death is attributed to progression of UC, "ulcerative colitis progression" should be recorded on the Adverse Event eCRF. If the death is attributed to progression of CD, "Crohn's disease progression" should be recorded on the Adverse Event eCRF.

Deaths that occur after the adverse event reporting period should be reported as described in Section 5.6.

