5.4.2.2 Events That Occur after Study Drug Initiation

After initiation of study drug following study entry or study re-entry, serious adverse events and adverse events of special interest will be reported until 8 weeks after the final dose of study drug. Investigators should record all case details that can be gathered immediately (i.e., within 24 hours after learning of the event) on the Adverse Event eCRF and submit the report via the electronic data capture (EDC) system. A report will be generated and sent to Safety Risk Management by the EDC system.

In the event that the EDC system is unavailable, the paper Clinical Trial Serious Adverse Event/Adverse Event of Special Interest Reporting Form provided to investigators should be completed and submitted to the Sponsor or its designee immediately (i.e., no more than 24 hours after learning of the event), by faxing the form using the fax number provided in Section 5.4.2.1. Once the EDC system is available, all information will need to be entered and submitted via the EDC system.

Instructions for reporting serious adverse events that occur >8 weeks after the final dose of study treatment are provided in Section 5.6.

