5.6 ADVERSE EVENTS THAT OCCUR AFTER THE ADVERSE EVENT REPORTING PERIOD

The Sponsor should be notified if the investigator becomes aware of any serious adverse event that occurs after the end of the adverse event reporting period (defined as 8 weeks after the final dose of study drug), if the event is believed to be related to prior study drug treatment. These events should be reported through use of the Adverse Event eCRF. However, if the EDC system is not available, the investigator should report these events directly to the Sponsor or its designee, by faxing the paper Clinical Trial Serious Adverse Event/Adverse Event of Special Interest Reporting Form using the fax number provided to investigators.

5.7 EXPEDITED REPORTING TO HEALTH AUTHORITIES, INVESTIGATORS, INSTITUTIONAL REVIEW BOARDS, AND ETHICS COMMITTEES

The Sponsor will promptly evaluate all serious adverse events and adverse events of special interest against cumulative product experience to identify and expeditiously communicate possible new safety findings to investigators, IRBs, ECs, and applicable health authorities based on applicable legislation.

To determine reporting requirements for single adverse event cases, the Sponsor will assess the expectedness of these events *through the use of the reference safety information in the document listed below:*

Drug	Document
Efmarodocokin alfa	Efmarodocokin Alfa Investigator's Brochure

The Sponsor will compare the severity of each event and the cumulative event frequency reported for the study with the severity and frequency reported in the applicable reference document.

Reporting requirements will also be based on the investigator's assessment of causality and seriousness, with allowance for upgrading by the Sponsor as needed.

Currently there are no expected serious adverse drug reactions for efmarodocokin alfa described in the Efmarodocokin Alfa Investigator's Brochure. Thus, any treatment-emergent serious adverse event deemed related to efmarodocokin alfa will be reported as a suspected unexpected serious adverse reaction (SUSAR). Reporting of individual SUSARs to investigators, IRBs, ECs, and applicable health authorities will be done in accordance with applicable legislation.

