- ¹ After informed consent for study entry has been obtained but prior to initiation of study drug, only serious adverse events caused by a protocol-mandated intervention should be reported. After informed consent for study re-entry has been obtained (see Section 3.1.3) but prior to initiation of study drug, only serious adverse events caused by a protocol-mandated intervention (e.g., invasive procedures such as biopsies, discontinuation of medications) or prior study treatment should be reported. After initiation of study drug following study entry or study re-entry, all adverse events will be reported until 8 weeks after the final dose of study drug. After this period, the Sponsor should be notified if the investigator becomes aware of any serious adverse event that is believed to be related to prior study drug treatment (see Section 5.6). Any adverse event that occurs after completion of Week 52 and required safety follow-up assessments but prior to obtaining informed consent for study re-entry should be captured on the General Medical History and Baseline Conditions eCRF rather than the Adverse Event eCRF, unless it is a serious adverse event related to prior study treatment.
- ^m Vital signs include measurements of respiratory rate, pulse rate, systolic blood pressure, diastolic blood pressure, and temperature. Patient should be in a seated position after at least 10 minutes of rest prior to measuring vital signs.
- ⁿ A complete physical examination includes evaluation of the head, eyes, ears, nose, and throat, and the cardiovascular, dermatologic, musculoskeletal, respiratory, gastrointestinal, genitourinary, and neurologic systems. Record abnormalities observed at baseline (Study Week 0) on the General Medical History and Baseline Conditions eCRF.
- ^o Perform a limited, symptom-directed examination, including an abdominal examination, at specified timepoints or as clinically indicated. Record new or worsened clinically significant abnormalities on the Adverse Event eCRF.
- ^p Patient must be resting in a supine position for at least 10 minutes prior to ECG assessment. ECGs are to be obtained prior to other procedures scheduled at that same time (e.g., vital sign measurements, blood draws) and should not be obtained within 3 hours after any meal if possible. ECGs should be performed at each dosing visit until after the shortest tolerated infusion delivery time is reached (i.e., infusion is tolerated without infusion-associated adverse event).

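### All-cause reporting of adverse events, serious events and deaths ends 8 weeks after an undefined 'final dose', although remitters may be observed off drug to Week 104

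*Combined protocol and SAP*

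**What the plan says.** Under Section 3.1.2 and Table 2, a patient in clinical remission stops efmarodocokin alfa and is observed, for up to about 2 years in the study. Treatment may start again later.

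The reporting rules share one limit:

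- Adverse events (Section 5.3.1, repeated in Appendix 1 footnote l): "all adverse events will be reported until 8 weeks after the final dose of study drug".
- Serious and special-interest events (Section 5.4.2.2): "serious adverse events and adverse events of special interest will be reported until 8 weeks after the final dose of study drug".
- Deaths (Section 5.3.5.9): "All deaths that occur during the protocol-specified adverse event reporting period" must be recorded and reported; later ones are referred to Section 5.6.
- After the limit, Section 5.6 asks for notice of a serious event only "if the event is believed to be related to prior study drug treatment". Footnote l says the same.

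Two places carry no time limit. Section 4.5.3 says: "New or worsened clinically significant abnormalities should be recorded as adverse events on the Adverse Event eCRF". Appendix 1 footnote o says: "Record new or worsened clinically significant abnormalities on the Adverse Event eCRF". Footnote o belongs to the limited physical examination, which is scheduled at the 8-weekly off-drug visits. Footnote e starts those visits 16 weeks after remission.

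**The concern.** The study's purpose is long-term safety. Section 1.3 wants the benefit-risk profile of an intermittent, treat-to-remission strategy, and Section 6.4 wants the effect of intermittent dosing. Both need events from drug-free periods as well as from dosing periods.

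As written, a death or serious event in a patient several months off drug is reported only if someone believes the drug caused it. A special-interest event that is not serious falls outside Section 5.6 altogether. Late off-drug counts are therefore filtered by causality judgement.

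The undefined term adds a second filter. If 'final dose' means the last dose in the study, a drug-free period is covered when the patient is later re-treated and not covered when the patient stays well. Capture then depends on a later outcome. The protocol itself names risks that could outlast 8 weeks: neutralizing anti-drug antibodies, with follow-up of up to 6 months after the last dose (Section 5.1.1.4), and epithelial tumor promotion (Section 5.1.1.3).

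**Working it through.** **1. The plan's own figures.** Section 6.1 gives 95% intervals of 3% to 12% and 8% to 20% for serious-event rates of 6.6% (13/198) and 13.5% (37/275) with n = 135. The Clopper-Pearson method gives 3.0% to 12.2% and 8.2% to 20.4%, so the stated intervals reproduce.

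**2. Dates.** Suppose remission is found when the next 4-weekly dose was due, for example last dose at Week 24 and remission at Week 28. All-cause reporting ends at 24 + 8 = Week 32. The follow-up visit 8 weeks after remission is at Week 36, which is 12 weeks after the last dose and already past the limit. The 8-weekly visits run from 28 + 16 = Week 44. Limited examinations fall at Weeks 36, 44, 52, 60, 68, 76, 84, 92 and 100. At these nine visits footnote o asks for an adverse event form entry after the reporting period has closed.

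**3. The two readings of 'final dose'.** With a last dose at Week 24 and a restart at Week 44, 60 or 80 (assumed), the last-of-course reading leaves 44 − 32 = 12, 60 − 32 = 28 or 80 − 32 = 48 weeks of the gap without all-cause reporting. The last-in-study reading leaves none of it. But Section 5.4 requires serious events within 24 hours, and at that point a site cannot know whether a dose will prove to be the last.

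**4. Size, as an illustration.** Assumptions:

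- 27 of 135 patients remit. The 20% in Section 6.1 is sustained remission at Week 52; here it is applied to remission found at Week 28.
- Last dose at Week 24, no restart and no dropout.
- Constant hazard at the Section 6.1 rates, which come from placebo arms in active ulcerative colitis.
- No late serious event judged related.

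Time outside all-cause reporting: 104 − 32 = 72 weeks per patient, and 27 × 72/52 = 37.4 patient-years. Of these, 27 × 20/52 = 10.4 fall in Year 1 and 27 × 52/52 = 27.0 (72%) in Year 2.

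Risk by week w: 1 − (1 − p)^(w/52), where p is the 52-week rate.

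| p | by Week 32 | by Week 104 | patients with first serious event after Week 32 |
|---|---|---|---|
| 6.6% | 4.11% | 12.76% | 27 × 8.65% = 2.3 |
| 13.5% | 8.54% | 25.18% | 27 × 16.64% = 4.5 |

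Pooled 52-week proportion captured: 0.8 × 6.6 + 0.2 × 4.11 = 6.1%, and 0.8 × 13.5 + 0.2 × 8.54 = 12.5%. The shifts are 0.5 and 1.0 point. With the last dose anywhere from Week 12 to Week 28, the captured values run from 5.8% to 6.2% and from 11.9% to 12.7%.

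**5. Sensitivity of the patient-years.**

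- No Year 2 participation: 10.4 patient-years, with 27 × (6.6% − 4.11%) = 0.7 to 27 × (13.5% − 8.54%) = 1.3 patients.
- Dropout of 20% per year, exponential from Week 0: a mean of 54.0 weeks outside the limit, and 27 × 54.0/52 = 28.0 patient-years.
- 10% remitting, last dose at Week 40: 13.5 × 56/52 = 14.5 patient-years.
- 30% remitting, last dose at Week 12: 40.5 × 84/52 = 65.4 patient-years.

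**The case against.** A reader might infer that the Appendix 1 adverse event row, ticked at every visit type, contradicts the limit. It does not. The row carries footnote l, which repeats the limit and adds: "After this period, the Sponsor should be notified if the investigator becomes aware of any serious adverse event" believed related to prior treatment. The ticks are needed to ask about those events.

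A reader might also set the opening of Section 5.3.1, "Investigators will seek information on adverse events at each patient contact", against the cut-off. That sentence is general. The rest of the section narrows it, and Section 5.3 makes the specific instructions govern. It is at most an ambiguity between recording and reporting.

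On 'final dose', the defence is that Section 5.3.1 never speaks of courses, while other sections say so when they mean one, and Section 3.1.3 uses 'last dose' where more treatment may follow. This favours the last-in-study reading but does not settle it. In Section 3.1.6, re-entering patients have already had safety follow-up after a final dose, are treated again, and repeat that follow-up.

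It is also fair that related-only reporting after 8 weeks is stated consistently and matches the safety follow-up visit. Off-drug safety data do not stop either: vital signs, hematology and chemistry continue at the 8-weekly visits, suspected malignancy goes to the sponsor (Section 5.1.2.3), and Table 6 defaults to 'related'. Section 6.4 plans no off-drug table as such. These points reduce the loss. They do not supply uniform reporting of deaths, serious events and special-interest events.

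**Conclusion.** The point stands as a gap in reporting, an undefined term and one firm inconsistency: Section 4.5.3 and footnote o against the 8-week limit. Under the last-of-course reading, every drug-free period beyond 8 weeks loses all-cause reporting. Under the last-in-study reading, only drug-free time that no later dose follows loses it, and this is known only in retrospect.

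It is tempting to conclude that sites will record late events differently. That is a possible consequence, but the documents do not say so, and the eCRF training and completion manual in Section 7.2 might settle practice. Nor is any planning figure wrong. The base-case shift of about 1 point or less lies well inside the stated intervals, and time on drug plus 8 weeks is unaffected.

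The 37.4 patient-years and 2.3 to 4.5 patients show scale only. Placebo-arm rates may not suit patients in remission, and counting no late event as related makes the patient numbers an upper figure for that scenario. The change is worth making because it is cheap and serves the study's main purpose.

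**What to change.** 1. Define 'final dose' as either the last dose of a course or the last dose in the study.
2. Reconcile Sections 5.3.1, 5.3.5.9, 5.4.2.2 and 5.6 and Appendix 1 footnote l with Section 4.5.3 and footnote o.
3. For every patient dosed in this study, report the following regardless of causality through the last study visit: serious adverse events, deaths, and the special-interest events in Section 5.2.3 that remain meaningful off drug (potential drug-induced liver injury, neurologic signs suggesting progressive multifocal leukoencephalopathy, COVID-19, and thromboembolism or deep vein thrombosis of Grade 2 or higher).
4. In Section 6.4, tabulate events within 8 weeks of a dose separately from later off-drug events, each with its time at risk.

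The cost is amendment wording and some extra entry of unrelated background events. The visits already take place and already list adverse events, so no visit or procedure is added.
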